3.3. Study Endpoints

3.3.1. Primary Endpoint

The primary endpoint is a description of the overall incidence and nature of treatment-emergent adverse events (TEAEs) during treatment weeks 5-50.

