9.1. Adverse Events

Details regarding the definition and reporting of an AE or a serious adverse event (SAE) are provided in the study protocol. AEs will be recorded starting with the signing of the first

informed consent. All AEs will be collected through the Washout and Safety follow up visit (or Early Termination Visit). Following the Washout and Safety follow up visit (or Early Termination Visit), all unresolved AEs that were reported by the Investigator to be probably drug related should be followed by the Investigator until the events are resolved, the patient is lost to follow-up, or the AE has stabilized.

Non-serious AEs that begin during the Observation Period will be captured as medical history in the TR03 extension study; patients who never transition from the Observation Period to the Treatment Period are screening failures and did not complete the early termination or end of study CRFs. SAEs occurring during the Observation Period will be recorded as SAEs.

Also, AEs that were ongoing at the time of a patient's completion of the TR03 core study are recorded as medical history in the TR03 extension study.

A treatment-emergent AE (TEAE) will be defined as one starting or worsening on or after the first dose of study medication during the extension study. If the start date is missing, the event is assumed to be treatment emergent.

For patients who complete study treatment through the Visit 14/End of Treatment visit, Titration Period AEs are those with an onset date from first dose date of the extension study through (first dose date + 27 days). Treatment Period AEs are those with an onset date from first dose date of the extension study through (first dose date + 349 days). Washout and Safety Follow-up AEs are those with an extension study onset date of (first dose date + 350 days) through (first dose date + 363 days). For patients who are treated and who discontinue study drug use prior to the Visit 14/End of Treatment visit yet remain on-study, AEs with an onset date on or after the first dose date of the extension study will be considered Treatment Period AEs.

For the purpose of inclusion in TEAE table summaries, incomplete AE onset and end dates will be imputed as described below.

For incomplete AE onset dates:

- If the day is missing but the month and year are known:
 - If the month and year are different from the month and year of the first dose of study drug, then use the first day of the month as the imputed onset date.

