 - If the month and year are the same as the month and year of the first dose of study drug, and the end date (after any imputation) is on or after the first dose of study drug, then use the date of the first dose of study drug as the imputed onset date.
 - If the month and year are the same as the month and year of the first dose of study drug, and the end date (after any imputation) is prior to the date of the first dose of study drug, then use the end date as the imputed onset date.
- If the month is missing but the year is known (day can be either missing or known):
 - If the year is different from the year of the first dose of study drug then use Jan. 1st of the reported year as the imputed onset date.

- If the year is the same as the year of the first dose of study drug and the end date (after any imputation) is on or after the first dose of study drug then use the date of the first dose of study drug as the imputed onset date.
- If the year is the same as the year of the first dose of study drug and the end date (after any imputation) is prior to the date of the first dose of study drug, then use the end date as the imputed onset date.
- If the start date is completely missing, the event is assumed to be treatment-emergent.

For incomplete AE end dates:

- If the day is missing but the month and year are known then use the last day of the month as the imputed end date.
- If the month is missing but the year is known (and the day is either missing or known) then use Dec. 31st of the year as the imputed end date.

Adverse events will be coded according to MedDRA (version to be delineated in the clinical study report).

All AE summary tables will present system organ class (SOC) and preferred term (PT), will include counts of patients, and will be based on TEAEs. SOC will be displayed in descending order of frequency overall and then alphabetically. PT will be displayed in descending order of frequency overall and then alphabetically within SOC. A patient with two or more AEs within the same level of summarization will be counted only once in that level using the most extreme incident. Percentages will be based on the number of patients in the safety population.

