9.1.1. Incidence of Adverse Events

An overview summary of the number and percentage of patients with any TEAE and the total number of TEAEs recorded will be presented for: patients experiencing any TEAE, any treatment-emergent SAE, any related TEAE, any TEAE by maximum intensity, and any TEAE by treatment period for the Treatment Period and Washout and Safety Follow-up Period.

The overview summary will be repeated for the Treatment Period and Washout and Safety Follow-up Period. For an AE that is reported during more than one of these periods, the earliest period of onset will be used in the incidence calculation. Additionally, the overview summary will be repeated for the Titration Period. Since the Titration Period is a subset of the Treatment Period, AEs will be reported in both periods, where applicable.

Summaries of the total number of TEAEs and the number and percentage of patients with at least one TEAE will be provided by SOC and PT.

A summary of the total number of AEs occurring during the Observation Period (captured in the TR03 extension study medical history form) and the number and percentage of patients with at least one AE during the Observation Period will be provided by body system and dictionary term. New medical history for the TR03 extension study (i.e. with an onset date on or after the signing of the informed consent for the TR03 extension study) is captured in the TR03 extension study medical history form.

All AEs will be presented in a data listing for the safety population.

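### The SAP's primary endpoint is TEAEs in treatment weeks 5-50, but no adverse-event window or period summary in its Section 9 isolates those weeks

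*SAP*

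**What the plan says.** Section 3.3.1 of the SAP defines the primary endpoint as a "description of the overall incidence and nature of treatment-emergent adverse events (TEAEs) during treatment weeks 5-50". Section 3.4 fixes the maintenance dose at the end of Treatment Week 4, so week 5 is where maintenance dosing starts. The primary objective in Section 2.1 is wider: safety and tolerability over a treatment period of up to 50 weeks, with no exclusion of weeks 1-4.

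Section 9.1 sets the windows for patients who complete through Visit 14. Titration runs from first dose to first dose + 27 days. For Treatment, "Treatment Period AEs are those with an onset date from first dose date of the extension study through (first dose date + 349 days"). Washout runs from + 350 to + 363 days. For patients who stop drug earlier but remain on study there is a single rule: "AEs with an onset date on or after the first dose date of the extension study will be considered Treatment Period AEs".

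Section 9.1.1 says of the overlap: "Since the Titration Period is a subset of the Treatment Period, AEs will be reported in both periods, where applicable". On denominators, Section 9.1 says: "Percentages will be based on the number of patients in the safety population". Section 4.11, which lists changes to the planned analysis, does not mention the primary endpoint.

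**The concern.** A primary endpoint needs a rule that says which events and which patients enter it. Here the endpoint names a span of weeks, and the section that turns events into tables never uses that span. A programmer who follows Section 9 exactly would produce whole-treatment, titration and washout summaries, and none of them would be the primary endpoint.

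At stake is the post-titration safety description that Section 3.3.1 singles out. Without a stated window it would either appear only mixed with events from weeks 1-4, or be derived later under rules chosen after the data are known: when the window ends, how early discontinuers are treated, and which denominator applies.

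**Working it through.** **1. Convert the windows.** With offset = days after first dose, study day = offset + 1 (Section 4.2) and week = floor(offset/7) + 1.

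| Window | Offsets | Study days | Weeks |
|---|---|---|---|
| Titration (9.1) | 0 to 27 | 1-28 | 1-4 |
| Treatment (9.1) | 0 to 349 | 1-350 | 1-50 |
| Washout (9.1) | 350 to 363 | 351-364 | 51-52 |
| Primary endpoint (3.3.1) | 4×7 = 28 to 50×7−1 = 349 | 29-350 | 5-50 |

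The endpoint window is 350 − 28 = 322 days long. None of the three defined windows equals it.

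**2. Check where the windows are used.** The overview (9.1.1), severity (9.1.3), special-interest (9.1.6) and abuse-potential (9.1.7) summaries are repeated for Treatment, Washout and Titration. Serious events (9.1.5) are split by Treatment and Washout. The relationship summary (9.1.2) and the summary of events leading to discontinuation (9.1.4) have no period split. No summary is specified for weeks 5-50.

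**3. Try subtraction.** Let A be the number of patients with a TEAE in Treatment, T the number in Titration, and X the number in weeks 5-50. Suppose first that the Titration window applied to every treated patient. A patient counted in T may or may not have a later event, and each patient counts once per level, so

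A − T ≤ X ≤ A.

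The interval is as wide as T. The SAP gives no event rates, so these inputs per 100 patients are assumed:

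| A | T | X lies between |
|---|---|---|
| 80 | 60 | 20 and 80 |
| 70 | 40 | 30 and 70 |
| 85 | 50 | 35 and 85 |
| 60 | 20 | 40 and 60 |

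The literal text is looser still. Section 9.1 defines Titration only for patients who complete through Visit 14. If E early discontinuers had an event in days 1-28, they count in A but not in T, and the lower limit falls to A − T − E. It can fall further, because the Treatment Period of an early discontinuer has no end date and takes in off-drug events. Event totals, as opposed to patient counts, can be subtracted for completers only.

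**4. Check the end of the window.** Under Section 3.1, observation plus treatment cannot exceed 50 weeks. A patient with k weeks of observation (k up to 12) therefore has at most 50 − k weeks on drug, and washout covers offsets 7(50 − k) to 7(50 − k) + 13. For k = 2 that is 336 to 349; for k = 12 it is 266 to 279. All 14 washout days then fall at or before offset 349. A fixed end at + 349 would count these off-drug days as treatment, so the new window needs an end tied to each patient's last dose.

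**5. Size the denominator effect.** If a share d stops before day 29 and the incidence among those still on drug is p, the Safety-population percentage for on-treatment events is p(1 − d). With assumed p = 50%:

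- d = 10%: 50 × 0.90 = 45%
- d = 20%: 50 × 0.80 = 40%
- d = 30%: 50 × 0.70 = 35%
- d = 40%: 50 × 0.60 = 30%

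The SAP does not give d. The failure-to-improve stop begins at the third treatment visit (3.2.1), which Section 7.3.1 places at week 5, so stops before day 29 would have to come from other causes.

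**The case against.** The best defence is that nothing is lost. The study is descriptive with no inference planned (4.3), every adverse event is listed, and onset dates would allow a weeks 5-50 summary at any time. The Treatment Period tables contain all on-treatment weeks 5-50 events and answer the primary objective as Section 2.1 words it. Section 4.1 refers to table shells that are not shown, so the gap can be asserted only of the SAP text. All of this stands, but it does not supply a specified analysis of the stated primary endpoint.

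A reader might infer more than the SAP supports on four points:

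- *System organ class and preferred term are never split by period.* They are, through the severity tables: Section 9.1 has every adverse-event table present both levels, and Section 9.1.3 repeats severity by period. What is missing is the weeks 5-50 cut.
- *Titration events would dominate the Treatment Period tables.* The SAP gives no data on event timing, and Section 3.4 bases titration on tolerability.
- *No denominator is defined.* Sections 4.6.2 and 9.1 give one, the Safety population. A day-29 at-risk set is a recommendation, not the correction of an error. It also selects patients who tolerated titration.
- *The trial would fail its purpose.* Objective and endpoint disagree on the span, so the SAP does not settle that the maintenance phase alone is the purpose.

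**Conclusion.** The point holds for the SAP text. Sections 3.3.1 and 9.1 do not match: the primary endpoint covers days 29-350, and the defined windows cover days 1-28, 1-350 and 351-364. No specified period summary reports the endpoint, and subtraction leaves patient incidence undetermined over a range at least as wide as the number of patients with a titration event. This conclusion rests on the SAP's own day counts and counting rules. The 20-to-80 example and the fall from 50% to between 45% and 30% rest on assumed inputs and show only the possible scale. Because it concerns the primary endpoint and is cheap to correct, it should be corrected before the analysis is run.

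**What to change.** 1. In Section 9.1 add a post-titration window for all treated patients: onset from first dose + 28 days to an end tied to each patient's last dose, or to a stated on-treatment cut-off, and not beyond week 50.
2. Apply the Titration window to early discontinuers as well as completers.
3. Produce the overview, system organ class/preferred term, severity and relationship tables on the new window and label them as the primary-endpoint tables. Keep the Titration and whole Treatment Period tables as supportive.
4. Reconcile Section 2.1 (up to 50 weeks) with Section 3.3.1 (weeks 5-50). If the whole treatment period is what is meant, say so and record the change in Section 4.11.
5. As a recommendation, show percentages among patients still on study drug at day 29 beside the Safety-population percentages. Exposure-adjusted rates from day 29 would be a reasonable optional addition, since maximum treatment runs from 50 − 12 = 38 to 50 weeks.

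The cost is SAP wording and one more run of tables already planned, using onset and last-dose dates already collected. The small downside of item 5 is that the day-29 subset is smaller and selected for having tolerated titration, which is why both denominators should be shown.

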3.3.2. Secondary Endpoints

Visit 1a or Visit 1b will serve as the baseline visit for efficacy endpoints. Visit 1a will be the Baseline for patients directly entering the Treatment Period as of Visit 1a. Visit 1b will be the Baseline for patients entering the Treatment Period after participating in the Observation Period for any length of time.

The secondary endpoints are:

- Assess skin lesion improvement using the metrics of the PAS
- Change from Baseline in PRO measures Worst itch NRS, average itch intensity NRS, VRS (itchy, burning and stinging), MOS-Sleep-R, ItchyQoL, HADS by Treatment Period study visit and Baseline NRS score
- Change between Baseline and the final Treatment Period visit in PBI-P
- A description of the percentage of patients utilizing various doses of nalbuphine HCl ER tablets by study week
- A description of the frequency and reasons for dose up-and down-titration and treatment discontinuation during the study
- Frequency and distribution by time on study of patients determined to meet failure-to-improve criterion
- Changes in the PRO measurements during the Washout Period after cessation of treatment of nalbuphine HCl ER tablets
- Time to first use of rescue medications and the number of days of use of rescue medications for itching
- To evaluate the daily changes in the SOWS during the Washout Period after cessation of treatment of nalbuphine HCl ER tablets.

3.3.3. Exploratory Endpoints

The exploratory objectives of the study are to evaluate the effect of nalbuphine HCl ER tablets on:

- The potential of nalbuphine HCl ER tablets to impact on the measurement of nerve fiber density (histology) and MOR/KOR density (histology, Western Blot), as well as histological (H&E) changes in skin biopsies taken at Baseline and the final TV when compared to biopsy material assessed during study TR03 (optional procedure at select sites only).

3.3.4. Safety Assessments

Safety assessments include the following:

- AEs
- Vital signs
 - Weight
 - Systolic blood pressure (SBP)
 - Diastolic blood pressure (DBP)
 - Heart rate (HR)
 - Respiration rate (RR)
 - Body temperature
- Physical examination
 - Clinically significant abnormalities pre-dose are reported as part of medical history
 - Clinically significant abnormalities representing a worsening from baseline, subsequent to dosing, are reported as AEs
- Neurological examination
- Clinical laboratory tests
 - Blood chemistry
 - Hematology
 - Urinalysis
 - Serum Pregnancy
- Investigator reviewed ECG and central cardiac core laboratory read 12 Lead-ECG cardiovascular grading, and/or cardiovascular related prohibited medications
- SOWS.

3.4. Treatments

Following enrollment, the patient will receive 30 mg open-label tablets. At each visit at which study drug is to be dispensed, enough drug should be supplied to ensure a sufficient number of tablets available for dosing until the next visit plus an additional 8 tablets to allow for visit windows and/or possibility of a missed visit.

Study drug can be taken with or without food. Patients will be instructed to take the AM and PM Study Drug tablets at the same times of the day, approximately 12 hours apart, preferably with 240 milliliters (mL) (approximately 8 ounces) of water. If the patient does not take a particular dose at the planned time he or she may take it up to 2 hours later. For example, if a patient is taking the Study Drug at 9 AM and 9 PM but forgets to take the 9 AM dose, the patient may take the 9 AM dose as late as 11 AM. After that time, the patient should skip the 9 AM dose and, instead, take the regularly scheduled next dose at 9 PM.

The first dosing day will be on either Visit 1a or Visit 1b. Titration will be based on tolerability. If the patient is experiencing a study-drug related AE or an AE that may be aggravated by study drug up-titration, the study drug dose should not be increased, regardless of the NRS score.

The Study Drug will be titrated during the Treatment Period Weeks 1 - 4, according to the schedule in Table 3 in the study protocol to a final dose of 30 mg BID up to 180 mg BID. The dosing for Treatment Week 1 is further described in Section 9.6.1 (Visit 1a) and Section 9.6.4 (Visit 1b) of the study protocol. Patients should only ever be dispensed a single strength of the study drug (e.g. 30 mg bottle(s) or 60 mg bottle(s)) at a visit.

Patients will titrate to tolerability beginning with a 30 mg dose on Day 1 (Visit 1a or Visit 1b) with a dose increase of 30 mg BID not more often than every 3 to 4 days in order to attain steady-state plasma concentrations of nalbuphine at each dose.

Patients should be instructed to up-titrate beginning with a single 30 mg dose in the evening (PM) and then begin dosing with an increased 30 mg BID dose the following day. Dose titrations should be maintained for 3-4 days before further up-titration of the patient's dose is attempted

The maximum dose the patient should reach at the end of Week 1 is 60 mg BID. If this dose is tolerated (as determined by the Telephone Contact 1 (TC1) assessment), an additional up-titration may be attempted during Week 2.

The maximum dose the patient should reach at the end of Week 2 is 120 mg BID. If this dose is tolerated (as determined by the TC2 assessment), an additional up-titration may be attempted during Week 3.

The maximum dose the patient should reach at the end of Week 3 is 180 mg BID. If this dose is tolerated, it should be maintained throughout Week 4.

The dose achieved as of the end of Treatment Week 4 will be maintained throughout the rest of the Treatment Period. This dose will be defined as the patient's "maintenance dose".

During Treatment Weeks 1-4, the decision to up-titrate the patient's dose should be made based on tolerance to study drug. If the tolerance level becomes unacceptable to either the patient or the Investigator, the dose should be reduced incrementally until tolerance is stabilized (reduce dose by 30 mg BID if at the 30 mg, 60 mg, 90 mg or 120 mg dose level and reduce by 60 mg BID if the patient is at the 180 mg dose level). Patients who do not tolerate the 180 mg BID should be down titrated to the 120 mg BID dose level and maintained there if stabilized.

Two single dose reductions or dose holds per patient is permitted during Treatment Period at the Investigator's discretion. If subsequent dose reductions or dose interruptions are needed, the Medical Monitor must be contacted. The duration of any dose hold must be discussed with the Medical Monitor.

4. Statistical Considerations

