7.3.2. Extent of Exposure

Duration of exposure is defined as the total number of days a patient is exposed to any study drug and will be presented as the total number of days from the first dose date to the last dose date: (date of last dose of study medication - the date of first dose of study medication + 1). The date of first dose and date of last dose are reported in the eCRF on the dosing history and study completion pages, respectively. If the last dose date on the study completion page is missing, or if a patient is lost to follow-up, the visit date at which drug was last returned will be used as the date of last dose.

The duration of exposure to study drug will be summarized using descriptive statistics for the safety population.

Patient exposure information will be presented in a listing for the safety population.

It should be noted that duration of exposure calculated in this fashion does not account for missing individual doses or dosing interruptions as recorded in the eCRF.

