7.3.3. Treatment Compliance

On the date of the first dose of study medication, the patient is expected to take only one dose (3 tablets) of study medication (in the evening). For the remainder of the study, patients should take two doses (6 tablets) of study medication each day (one in the morning and one in the evening).

At designated visits (i.e. Weeks 1, 3, 5, 9, 13, 17, 21, 26, 30, 34, 38, 42 and 46) patients will be distributed bottles containing study medication. Patients will return the bottles at a subsequent study visit, as instructed.

The number of tablets taken will be derived as: (total tablets dispensed across visits – total tablets returned across visits) and will be used to assess overall study compliance.

The total number of tablets planned will be derived as:
 $3 + (\text{number of days between day after first dosing day and last dosing day, inclusive}) * 6$.

Patient compliance over the entire time interval from first day of treatment until the last reported dosing date will be derived as: $(\text{number of tablets taken}/\text{number of tablets planned}) * 100\%$. Patient study compliance will be summarized using descriptive statistics overall for the safety population.

Patient compliance information will be presented in a data listing for the safety population.

8. Secondary Endpoint Analysis

Efficacy measurements will be evaluated as secondary endpoints in this study. The safety population will be used to evaluate the efficacy endpoints defined for this study. Eligibility for analysis of a particular endpoint will require only that the patient have a baseline value and at least one post-baseline value so that a change from baseline calculation can be obtained. All efficacy endpoints will be evaluated through the generation of descriptive summary statistics. For continuous variables, the mean, standard deviation, median, minimum, and maximum will be presented for a particular visit and for the change from baseline (Visit 1a or 1b). For categorical variables, the number and percentage of patients within each category of classification will be summarized by study visit. No formal statistical testing will be conducted.

Visit 1a or 1b will serve as the baseline visit for efficacy endpoints. Visit 1a will be the baseline for patients directly entering the Treatment Period as of Visit 1a and Visit 1b will be the baseline for patients entering the Treatment Period after participating in the Observation Period for any length of time.

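### The compliance formula in SAP Section 7.3.3 plans six tablets for every calendar day, so it ignores permitted dose holds and, with larger effect, the titrated dose and tablet strength

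*SAP*

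**What the plan says.** **Holds and dosing (Section 3.4).** The SAP states: "Two single dose reductions or dose holds per patient is permitted during Treatment Period", at the investigator's discretion. Further reductions or interruptions require contact with the Medical Monitor. No hold length is fixed: "The duration of any dose hold must be discussed with the Medical Monitor". Patients start on 30 mg tablets, begin with a 30 mg dose on Day 1, and are titrated over four weeks to a final dose between 30 and 180 mg BID. Only one strength is dispensed at a visit, with 30 mg and 60 mg bottles given as examples.

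**Compliance (Section 7.3.3).** The section expects one dose of 3 tablets on the first day and 6 tablets on each day after that, for every patient. Tablets planned are 3 plus 6 times the "number of days between day after first dosing day and last dosing day, inclusive". Tablets taken are those dispensed minus those returned. Compliance is taken over planned, as a percentage over the whole interval from first to last dose. It is summarised descriptively and listed.

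**Exposure (Section 7.3.2).** The text opens: "Duration of exposure is defined as the total number of days a patient is exposed to any study drug". It then fixes the calculation as "date of last dose of study medication - the date of first dose of study medication + 1". It ends by noting that this duration "does not account for missing individual doses or dosing interruptions as recorded in the eCRF".

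**The concern.** Section 3.4 makes dose holds part of planned conduct. A held day followed by resumed dosing adds 6 tablets to the compliance denominator and nothing to the numerator. The reported percentage then mixes doses the patient failed to take with doses the patient was told not to take. Section 7.3.2 warns the reader about interruptions, but Section 7.3.3 does not.

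The same denominator assumes a constant 6 tablets a day, which does not fit the dosing in Section 3.4. The mismatch begins on Day 1: a 30 mg dose in 30 mg tablets is one tablet, whereas Section 7.3.3 plans three. Depending on dose and strength, the number of tablets a patient is told to take may be well below or well above 6 a day.

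At stake is whether the compliance table in a long-term safety and tolerability study can be read as adherence at all. As written, it largely reflects the dose level and tablet strength a patient was on.

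**Working it through.** The SAP gives no compliance or exposure figure to reproduce, so its formulas are applied directly.

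**Inputs**
- Span D = 50 weeks × 7 = 350 days, the maximum time on drug (Section 3.1). A 90-day span is added as an assumed shorter case.
- Planned = 3 + 6 × (D − 1); taken = dispensed − returned (Section 7.3.3).
- Exposure = last dose date − first dose date + 1 (Section 7.3.2).
- Total hold length h is not in the SAP. Assumed: 1, 7, 14 and 28 days, inside the span and followed by resumed dosing, with full adherence on all other days and all unused tablets returned.
- Doses of 30 to 180 mg BID and strengths of 30 and 60 mg (Section 3.4). The SAP does not say which strength goes with which dose, so every whole-tablet combination of the doses below is shown.

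**Step 1: effect of holds at 6 tablets a day.** Planned = 3 + 6 × 349 = 2,097. Taken = 2,097 − 6h. Days on drug = 350 − h. Overstatement of days on drug = 350/(350 − h) − 1.

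| Hold (days) | Taken | SAP compliance | Days on drug | SAP exposure | Overstatement |
|---|---|---|---|---|---|
| 1 | 2,091 | 99.7% | 349 | 350 | 0.3% |
| 7 | 2,055 | 98.0% | 343 | 350 | 2.0% |
| 14 | 2,013 | 96.0% | 336 | 350 | 4.2% |
| 28 | 1,929 | 92.0% | 322 | 350 | 8.7% |

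Removing 6h from the planned total returns 100% in every row.

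For a 90-day span, planned = 3 + 6 × 89 = 537. Holds of 7, 14 and 28 days give 495/537 = 92.2%, 453/537 = 84.4% and 369/537 = 68.7%.

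**Step 2: effect of the fixed tablet count, no hold.** Let t = 2 × dose / strength be the tablets per day, with t/2 on the first day. Ignoring titration, taken = t/2 + 349t = 349.5t. Planned = 2,097 = 349.5 × 6. Compliance for a fully adherent patient is therefore t/6.

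| Dose (BID) | 30 mg tablets | 60 mg tablets |
|---|---|---|
| 30 mg | 2 a day: 33.3% | – |
| 60 mg | 4 a day: 66.7% | 2 a day: 33.3% |
| 90 mg | 6 a day: 100% | – |
| 120 mg | 8 a day: 133.3% | 4 a day: 66.7% |
| 180 mg | 12 a day: 200% | 6 a day: 100% |

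Of these combinations, only 90 mg BID on 30 mg tablets and 180 mg BID on 60 mg tablets give the correct 100%.

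**Step 3: both together.** At 120 mg BID on 30 mg tablets with a 14-day hold, taken = 8 × (349.5 − 14) = 2,684, and 2,684/2,097 = 128.0%. Taking only the held days out of the denominator gives 2,684/(2,097 − 84) = 133.3%. Correcting for holds alone does not make the figure valid.

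**The case against.** Several stronger readings are tempting, and the SAP does not support them.

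- **That exposure is miscalculated or contradictory.** A reader might set the opening words of Section 7.3.2 against its formula. But the same sentence fixes the measure as the first-to-last-dose span, and the section discloses that interruptions are not removed. This is a defined duration with a stated limitation. A net-of-holds figure would be an addition, not the correction of an error.
- **That patients who follow a hold are classed as non-compliant.** Section 7.3.3 has no cut-off, and no population or other analysis depends on compliance. As Step 3 shows, a patient with a hold can still be above 100%.
- **That adverse event incidence is distorted.** Section 9.1 bases percentages on the number of patients in the safety population. No exposure-adjusted rate is planned.
- **That the 6- and 9-month treatment groups should use net exposure.** The SAP does not say how those months are derived, and Sections 8.1.3 and 8.1.5 count completers in every duration group. Netting out holds could conflict with that. A completer with 40 weeks on treatment and a 28-day hold has 280 − 28 = 252 net days, short of nine months (9/12 × 365.25 ≈ 274 days), yet must be counted there.
- **That holds fall mainly on patients who tolerate the drug poorly.** This is plausible, but Section 3.4 says only that holds are at the investigator's discretion.

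It is also fair to say that the compliance formula does what its own sentence announces, namely to cover the whole interval. A hold that ends in discontinuation generally falls after the last dose and adds nothing, except possibly where the drug-return visit date replaces a missing last-dose date. Missed doses are listed (Section 7.3.1), and dosing changes are tabulated by reason (Section 8.3). Short holds over a long span move the figure very little.

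None of this answers the core point. The denominator is called tablets planned, but for many patients it is not the number they were instructed to take, and no caveat says so.

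**Conclusion.** The point holds for the compliance formula in Section 7.3.3. Permitted holds followed by resumed dosing lower the percentage of a fully adherent patient, from 99.7% for one held day to 92.0% for 28 held days over 350 days, and by more over a shorter span. These figures rest on assumed hold lengths and on 6 tablets a day. The fixed 3/6-tablet rule distorts more: 33.3% to 200% for fully adherent patients without holds, ignoring titration and allowing any whole-tablet pairing of dose and strength. How many patients are affected cannot be known from the SAP.

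The consequence is confined to one descriptive summary and its listing. It is worth correcting because the stated rule yields a wrong number, and the SAP says that interruptions are in the eCRF. The exposure duration in Section 7.3.2 stands as a disclosed convention. It exceeds days on drug by 2.0% for 7 held days and 8.7% for 28 held days in 350, which justifies an extra row but not a charge of error.

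**What to change.** - **Section 7.3.3.** Replace the fixed formula. For each day from first to last dose, set tablets planned to the patient's prescribed daily dose divided by the strength dispensed, with only the doses due on the first day. Set it to zero on hold days recorded in the eCRF, and sum over days. The statement that every patient takes 3 and then 6 tablets must be reconciled with the dosing and tablet strengths in Section 3.4. Removing held days is necessary but not sufficient.
- **Section 7.3.2 (secondary).** Keep the first-to-last-dose duration and its caveat, and add a row for days on drug net of recorded holds.
- **No change** is needed to the adverse event percentages, and none is proposed for the 6- and 9-month categories.

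The cost is SAP wording and a few derived variables. The SAP says that interruptions are recorded in the eCRF and that dispensing, return and dosing-change data will be listed. It is assumed that the dispensing records identify tablet strength.
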